6.5.6 ECG

A standard 12-lead ECG will be obtained as follows (Table 6-1 and Table 6-3):

- At Visit 1 to assess eligibility for study entry (all patients)
- Visit 3 and Visit 15 during first dose monitoring of the Core and Extension Phase: two ECGs will be performed. The first ECG will be performed prior to the study drug administration and the second ECG will be performed post-dose, approximately at the end of the 6-hour monitoring period.
- At any visit if a dose-increase or restart of study drug is to occur as specified in Section 5.5.5, with first dose monitoring as above and in Appendix 2.
- Other scheduled visits (all patients) according to Table 6-1 and Table 6-3.

Digital ECG devices will be provided to each clinical site by the central ECG reader for the duration of the study. Detailed information about recording and transmission of the studies will be outlined in the study specific manual provided by the center reader.

ECG criteria that require permanent study drug discontinuation are listed in Section 5.5.9.

6.5.7 Pulmonary Function Tests

Pulmonary function tests evaluating FEV₁, FVC and D_LCO will be performed according to the visit schedule in Table 6-1, Table 6-2 and Table 6-3. During the study, if the patient reports any respiratory symptoms such as dyspnea, shortness of breath, chest tightness or wheezing, or pulmonary function test abnormalities, please refer to Appendix 3 for monitoring guidance.

The tests will be conducted in all patients who are enrolled into the study and in the manner consistent with the standard laboratory practice.

Spirometry

The technician should demonstrate the appropriate technique to the subject and follow the standard procedure for the pediatric population. The quality of the tests must be accounted for including the technicians' comments (especially when, despite proper coaching of the subject, full collaboration cannot be achieved).

A minimum of 3 acceptable maneuvers will be performed at each visit. The acceptability criteria are a satisfactory start of test and a satisfactory end of test. In addition, the technician should observe that the subject understood the instructions and performed the maneuver with a maximum inspiration, a good start, a smooth continuous exhalation and maximal effort. The largest FVC and the largest FEV₁ will be recorded, after examining the data from all of the acceptable curves, even if the 2 values do not come from the same curve.

For each test (FEV₁, FVC, D_LCO), the absolute value as well as the percent of predicted value will be recorded in the eCRF. FEV₁/FVC ratio (expressed in %) will be calculated centrally.

Forced expiratory volume in 1 second (FEV₁) and Forced vital capacity (FVC):

The FEV₁ describes the volume (in Liters) that is expelled within one second of forced expiration after a maximal inspiration and reflects the large airway resistance. A decrease in FEV₁ serves as a good parameter for detection of an obstructive ventilatory defect.

The FVC denotes the volume of gas (in Liters) that is exhaled during a forced expiration starting from a position of full inspiration and ending at complete expiration. This parameter is normal or might be slightly decreased in obstructive disease, but shows a mild to severe decrease in restrictive disease.

Diffusion capacity of carbon monoxide (D_LCO):

Gas exchange is assessed by the carbon monoxide diffusing capacity (DLCO) evaluated by the single breath holding method. It is a measurement of carbon monoxide (CO) transfer from the lung over a breath-holding period to pulmonary capillary blood. Because the CO binds readily to hemoglobin, the diffusion capacity needs to be corrected for hemoglobin in order to reflect an altered lung gas transport rather than altered hemoglobin.

The average of at least 2 acceptable tests that meet the repeatability requirement of either being within 3 ml CO/min/mmHg (or 1 mmol/min/kPa) of each other or within 10% of the highest value should be reported.

A D_LCO test is acceptable if it fulfills all the following criteria:

- Use of proper quality-controlled equipment
- Inspired volume of >85% of largest vital capacity in < 4 seconds
- A stable calculated breath hold for 10±2 seconds. There should be no evidence of leaks, or Valsalva, or Mueller maneuvers
- Expiration in <4 seconds (and sample collection time <3 seconds), with appropriate clearance of dead space and proper sampling/analysis of alveolar gas

All values must be corrected for hemoglobin concentration.

The DLCO can be expressed in both CI conventional units: ml CO/min/torr (or ml CO/min/mmHg), and SI units: mmol CO/min/kPa (Conversion factor: SI units x 2.986 = CI units).

6.5.8 Columbia Suicide Severity Rating Scale (C-SSRS)

The C-SSRS, a questionnaire that prospectively assesses Suicidal Ideation and Suicidal Behavior using a semi-structured interview to probe patient responses, must be administered according to [Table 6-1](#) and [Table 6-3](#) and also at unscheduled visits.

If, at any time after screening and/or baseline, the score is “yes” on item 4 or item 5 of the Suicidal Ideation section of the C-SSRS or “yes” on any item of the Suicidal Behavior section, the patient **must** be referred to a mental health care professional for further assessment and/or treatment. The decision on whether the study treatment should be discontinued is to be taken by the investigator in consultation with the mental health care professional to whom the patient is referred.

The C-SSRS will be administered by an IVR system with the patient entering responses directly into the IVR system. For patients unable/unwilling to do so or where self-reporting by minors is not permitted by the local regulatory authority, and for all patients below the age of 12, another individual (e.g. parent/other family member/caregiver/qualified site staff) will enter the answers to the C-SSRS questions into the IVR system on behalf of the patient.

The investigators must review reports received from the system for any answers indicative of suicidal ideation and adverse events on the Visit day the questionnaire was performed and before the patient is discharged. Adverse events ascertained through the administration of the C-SSRS will be documented.

6.6 Pregnancy and assessments of fertility

Females of child-bearing potential are defined as all females physiologically capable of becoming pregnant. This includes female children and adolescents who are menarchal or who become menarchal during the study.

Serum pregnancy test will be performed by the central laboratory for all females of child-bearing potential according to the schedule in [Table 6-1](#) and [Table 6-3](#).

Although it is expected that this study will enroll mostly girls who are not sexually active, some may be sexually active. All menarchal girls and their parents/caregivers should be informed about the potential risks of pregnancy and the need to prevent pregnancy during the study.

It is important to be sensitive in introducing this issue, as understanding and comprehension of a child about puberty, sexual activity, pregnancy and contraception varies with age. These discussions with the patient and her parents/caregivers are therefore best performed by investigators familiar with the child/adolescent and her family and are part of the circle of care. The investigator should also discuss the management of the pregnancy test results with the patient and her parents/caregivers. These discussions may vary across countries and regions and should be guided by requirements of the local regulatory authority.

Female patients of childbearing potential who are sexually active will perform a urine pregnancy test (e.g. via home pregnancy test kit) monthly (in the months between clinic Visits and serum pregnancy testing). In the event of a positive urine pregnancy test, the patient must immediately contact the investigator. Additional pregnancy tests may be performed at the investigator's discretion during the study. Patients becoming pregnant must discontinue study drug.

[figure not shown]
Female patients of child-bearing potential must be informed of the potential teratogenic risk with fingolimod and the need for highly effective contraception to prevent pregnancy while on study drug and for 2 months after stopping study drug should they be or become sexually active.

Use of a combination of any two of the following methods of contraception (a+b or a+c or b+c) should be used as appropriate:

- a) use of oral, injected or implanted hormonal methods of contraception
- b) placement of an intrauterine device or intrauterine system
- c) barrier methods of contraception: condom or occlusive cap (diaphragm or cervical/vault caps) with spermicidal foam/gel/film/cream/vaginal suppository

Contraception must be used during the study and for 2 months after stopping study drug. The decision on the contraceptive method should be reviewed at least every 3 months to evaluate the individual need and compatibility of the method chosen.

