4.1 Inclusion criteria

Core Phase:

Patients eligible for inclusion in this study have to fulfill all of the following criteria:

1. Written informed consent must be obtained before any assessment is performed.

2. Male and female patients aged 10-17 years old*, inclusive (i.e., have not yet had their 18th birthday) at randomization.
3. A diagnosis of MS as defined by the revised consensus definition for pediatric MS, ([Krupp et al 2013](#), [Polman et al 2011](#)).
4. Central review of the diagnosis of pediatric MS will be required for all patients prior to randomization.
5. At least one MS relapse/attack during the previous year or two MS relapses in the previous two years prior to screening or evidence of one or more Gd enhancing lesions on MRI within 6 months prior to randomization (including screening MRI).
6. Expanded Disability Status Scale (EDSS) score of 0 to 5.5, inclusive.

*Exception: If, in a specific country, use of interferon- β -1a IM in children below a certain age is included in the Contraindications section of Avonex (interferon- β -1a IM) local product information, inclusion of such patients is not permitted in that country. E.g. the Russian Avonex product information lists use in children below the age of 12 years as a contraindication.

Fingolimod Extension Phase:

Criterion applies to all patients entering the Extension Phase.

1. Patients that originally met Core Phase Inclusion criteria and completed the Core phase on or off of study drug.

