Fingolimod Extension Phase:

Criteria apply to patients who completed the Core Phase, but prematurely discontinued study drug.

1. Premature discontinuation of the study drug during the Core Phase due to:
 - an adverse event,
 - serious adverse event,
 - laboratory abnormality
 - other conditions leading to permanent study drug discontinuation due to safety reasons as described in protocol [Section 5.5.9](#).

Note: If a patient was discontinued due to lack of efficacy in the Core Phase, the patient may be offered the option to enter the extension trial if the investigator determines it is in the patient’s best interest when considering all available treatment options.

2. Patients with known new events or concomitant medications (washout periods required prior to Visit 15) that would exclude them from the Core Phase exclusion criteria. Serological or other additional tests will not be required.

5 Treatment

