A neuroradiologist will be responsible for:

- Previewing each MRI scan performed for the study patients
- Contacting the Primary Treating Physician in case of unexpected findings detected on the MRI scan

Ophthalmologist

- The Ophthalmologist will perform the ophthalmic examinations as per protocol

Pulmonary Function Test Laboratory Technician

- Pulmonary function test (PFT) technician will perform PFTs per local standard practice for pediatric patients

6 Visit schedule and assessments

The Core Phase will consist of two periods: a pre-randomization period consisting of screening and baseline visits, and a double-blind treatment period. The Extension Phase consists of a fingolimod treatment period.

The day of randomization in the Core Phase is defined as Day 1 of the study (Visit 3), which is the first day of study drug administration. Entry in the Extension Phase occurs at Visit 15 immediately following the completion of the Core Phase.

[Table 6-1](#), [Table 6-2](#) and [Table 6-3](#) lists all assessments and indicates with an “X” the visits when they are performed.

Patients should follow the visit schedule with an allowed visit window as follows:

- ± 2 days for Visit 4 and Visit 16
- ± 5 days for Visit 5 and all monthly visits
- ± 10 days for all quarterly and biannual visits
- + 14 days for Visit 15 (should be completed within 14 days of completion of Visit 14 / EOS-CP). Date of completion of Core Phase should be entered in the Study phase completion eCRF (date entered should be 1 day before Visit 15; first Extension Phase visit). Study drug should not be interrupted between the end of the Core Phase and the start of the Extension Phase.

Visit windows can be extended on a case-by-case basis to accommodate scheduling (please consult Sponsor for approval). The pre-randomization period may be extended with approval from the sponsor on a case by case basis to accommodate additional time needed to complete the screening assessments (e.g., additional lab tests, time to be (re)vaccinated, time to allow lab parameters to come within protocol requirements, etc.).

In addition to the scheduled visits, patients may have unscheduled visits following an onset of an MS relapse or for safety follow-up.

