Patients who prematurely discontinue study drug during the Core Phase should be encouraged to remain in the study. Patients who prematurely withdraw (PPW – Premature Patient Withdrawal) from the study for any reason should be scheduled for a final Visit 14 (EOS-CP) assessment at the time of discontinuation from study drug as outlined in [Table 6-1](#)). A follow-up visit should then be scheduled three months after the last dose of the study drug. If the patient is unable to return to the site for the Visit 14 / EOS-CP assessments, every effort should be made to contact the patient by telephone for safety evaluations during the 3 months

following the last dose of study drug, including a final contact at the 90-day point (3-month follow up).

Patients who prematurely discontinue study drug (SDD) during the Core Phase, and remain in the study will follow an abbreviated schedule of assessments (see [Table 6-2](#)). At the time of SDD, patients must complete the Visit 14 / EOS-CP assessments (as end of treatment assessments), followed by a 3-month follow-up visit prior to continuing in the abbreviated schedule of assessments. If a patient who is being followed in the abbreviated schedule of assessments prematurely withdraws from the study, the patient should be scheduled for a final visit (EOS-CP according to [Table 6-2](#)) at the time of study discontinuation.

Patients who have completed the Core Phase, as per [Table 6-1](#) or [Table 6-2](#), may be eligible to enter the long-term extension study ([Table 6-3](#)). Patients who complete the Core Phase on study drug, but choose not to enter the Extension Phase should return for a 3-month follow-up visit.

Patients who prematurely discontinue study drug (SDD) during the Extension Phase, may remain in the study and be followed at yearly visits (see [Table 6-2](#)). At the time of SDD, patients must complete the Visit 30 assessments (as end of treatment assessments), followed by a 3-month follow-up visit.

Table 6-2 Core Phase: Abbreviated schedule of assessments for patients with SDD

Phase	Double-blind Treatment Phase						
Visit No. ¹	8	9	10	11	12	13	14/ EOS-CP
Study month	6	9	12	15	18	21	24
Physical exam	X		X		X		X
Skin exam							X
[REDACTED]							
Pulmonary Function Tests	X		X		X		X
MS relapses	X	X	X	X	X	X	X
MS treatment/Concomitant medications/Steroids	X	X	X	X	X	X	X
EDSS	X	X	X	X	X	X	X
MRI	X		X		X		X
[REDACTED]							
Vital signs	X	X	X	X	X	X	X
Hematology/Blood chemistry	X		X		X		X
[REDACTED]							

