Urinalysis	X		X				X
C-SSRS ⁴	X	X	X	X	X	X	X
AE/SAE reporting (if any)	X	X	X	X	X	X	X
1. The abbreviated schedule should be adopted at the appropriate visit after the 3 month follow-up visit. [REDACTED]							
4. To be completed at every visit including any unscheduled visits.							

Table 6-3 Fingolimod Extension Phase: Assessment schedule

Phase	Fingolimod Treatment											
Visit No. #	15	16	17	18	19	20	21	22	23 to 29	Study Completion (Visit 30)***	FU ²	
Study month #	Day 1 ₁	1/2	1	2	3	6	9	12	every 6 months ¹⁵	60		
Incl/exclusion criteria	X											
Concomitant medications	X	X	X	X	X	X	X	X	X	X	X	
Pregnancy test (serum) ^{3**}		X	X	X	X	X	X	X	X	X	X	
Physical exam					X	X		X	1 / year	X	X	
Skin Exam									1 / 2 years	X		
Ophthalmologic Examination ₆					X	X		X	As Needed	X		
Pulmonary Function Tests			X		X	X		X	As Needed	X		
Vital signs	X	X	X	X	X	X	X	X	X	X	X	
Hematology/ Blood chemistry		X	X	X	X	X	X	X	X	X	X	
Urinalysis						X		X	1 / year	X		
Fingolimod drug supply ⁷	X			X	X	X		X	X			
ECG	X ⁸		X					X	1 / year	X		
MRI						X		X	1 / year ⁹	X		
EDSS ¹⁰					X	X	X	X	X	X	X	
MS relapse ¹¹	X	X	X	X	X	X	X	X	X	X	X	
C-SSRS ¹²	X	X	X	X	X	X	X	X	X	X	X	
Adverse events/SAEs ¹³	X	X	X	X	X	X	X	X	X	X	X	
Pharmacokinetic sample FTY720/FTY720-P ¹⁴			X									
First Dose Administration*	X			X ¹⁴	As needed							

Phase	Fingolimod Treatment										
Visit No. #	15	16	17	18	19	20	21	22	23 to 29	Study Completion (Visit 30)***	FU ²
Study month #	Day 1 1	1/2	1	2	3	6	9	12	every 6 months ¹⁵	60	

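### Females of child-bearing potential who enter the Extension from the off-drug schedule (Table 6-2) have no visible required pregnancy test close to their first Extension fingolimod dose

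*Protocol*

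**What the plan says.** **Route into the Extension.** Protocol Section 6 states that patients who stop study drug in the Core Phase "and remain in the study will follow an abbreviated schedule of assessments" (Table 6-2). They first complete the end-of-treatment assessments and a 3-month follow-up visit. The Extension inclusion criterion in Section 4.1 admits "Patients that originally met Core Phase Inclusion criteria and completed the Core phase on or off of study drug". Extension exclusion 1 (Section 4.2) bars those who stopped for an adverse event, a laboratory abnormality or another safety reason. A note allows those who stopped for lack of efficacy.

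**Pregnancy testing.** Section 6.6 says: "Serum pregnancy test will be performed by the central laboratory for all females of child-bearing potential according to the schedule in" Tables 6-1 and 6-3. Section 6.5.4 names the same two tables. In Table 6-3 the row beginning "Pregnancy test (serum" is empty at Visit 15 (Extension Day 1, first dose) and first marked at Visit 16. Monthly urine tests are for sexually active patients. Further tests are at the investigator's discretion.

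**Eligibility check at entry.** For patients who stopped drug, Extension exclusion 2 re-applies the Core exclusions to known new events and medications, then adds: "Serological or other additional tests will not be required". The synopsis has the same clause.

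**The concern.** Section 6.6 acknowledges a potential teratogenic risk with fingolimod. Elsewhere it orders serum testing for every female of child-bearing potential, whether or not she reports sexual activity. Patients coming from Table 6-2 have been off study drug and are about to be exposed to fingolimod again, or for the first time if they had been on interferon. That is when a current negative test matters most, and on the legible text it is the one point in this route where none is required.

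The eligibility rule does not fill the gap. Core exclusion 20 defines pregnancy by a positive HCG laboratory result, yet Extension exclusion 2 screens for it only as a known event and waives new tests. At stake is early fetal exposure in a girl whose pregnancy nobody has had reason to suspect.

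**Working it through.** No sample-size or power figure is involved. The check is a reading of the two schedules, followed by simple date arithmetic.

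**1. Is the blank at Visit 15 odd in itself?** No. Table 6-3 has 11 visit columns. The pregnancy row and the "Hematology/ Blood chemistry" row have the same pattern: empty at Visit 15 and marked in the other 10. Rows of this kind rely on the end-of-Core visit (EOS-CP) for the pre-dose value.

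**2. Does Table 6-2 supply that value?** Ten legible Table 6-3 rows are empty at Visit 15:

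| Table 6-3 row empty at Visit 15 | Legible mark at Table 6-2 EOS-CP? |
|---|---|
| Physical exam, skin exam, pulmonary function, hematology/chemistry, urinalysis, MRI, EDSS (7 rows) | Yes |
| Ophthalmologic exam | No, but Table 6-3 footnote 6 places OCT at EOS-CP |
| PK sample | No; taken at Month 1 of the Extension by design |
| Serum pregnancy test | No, and no explanation is legible |

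The count is 7 + 3 = 10. Table 6-2 has 12 legible rows, all marked at EOS-CP. None is a pregnancy test. Three further rows are redacted.

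**3. What do the cross-references add?** Section 6.5.4 sends blood chemistry to Tables 6-1, 6-2 and 6-3 but, in the same paragraph, pregnancy testing only to 6-1 and 6-3. This is corroboration, not proof: Section 6.5.8 also leaves Table 6-2 out for the C-SSRS, yet Table 6-2 has a C-SSRS row.

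**4. When is the first scheduled serum test after re-exposure?** Visit 16 is 2 weeks after Extension Day 1 (Section 3.1), with a window of ± 2 days (Section 6):

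- Sample: 14 − 2 = 12 to 14 + 2 = 16 days after the first dose.
- Result: Section 6.5.4 gives 48 hours after laboratory receipt as the earliest. So 12 + 2 = 14 to 16 + 2 = 18 days, plus shipping.

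**5. Is there room for a test before dosing?** Visit 15 "should be completed within 14 days of completion of Visit 14 / EOS-CP". A serum sample at EOS-CP uses at least 2 of those 14 days, leaving up to 14 − 2 = 12 for shipping. If Visit 15 follows the next day, as the protocol prefers, a central serum result cannot arrive in time, and an on-site urine test is the workable choice.

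**The case against.** The strongest objection is that absence is being inferred from tables that cannot be read in full. Table 6-1 is not in the available text. Table 6-2 has redacted rows and a redacted stretch in its footnotes (numbering runs from 1 to 4). In Table 6-3, footnotes 4 and 5 are redacted and no row carrying them is visible, so the number of visible redaction marks does not limit what is hidden. Footnote 6 also places OCT at EOS-CP although Table 6-2 shows no legible row for it. An assessment can therefore be planned at EOS-CP without being visible there. All this stands, and it limits the claim. A hidden pregnancy row still looks unlikely, because the same row is printed openly in Table 6-3. The redacted row next to hematology fits endocrinology, which Section 6.5.4 assigns to Table 6-2.

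A second objection is that other safeguards exist:

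- Core exclusion 21 (abstinence, or contraception if sexually active), carried over through Extension exclusion 2.
- Contraception during the study, with the choice of method reviewed at least every 3 months (Section 6.6).
- Monthly urine tests for sexually active girls, which are not expressly limited to time on drug.
- Not entering girls whose compliance with contraception is in doubt (Section 10.2), and sexual activity without agreed contraception as a ground for stopping drug (Section 5.5.9).

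These make an undetected pregnancy at Visit 15 unlikely, and Section 6.6 expects most girls not to be sexually active. None of them requires a negative result before the dose. The urine tests depend on sexual activity being known.

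A reader might infer that these girls start fingolimod never having been tested. The documents do not support that. End-of-treatment assessments at discontinuation and a 3-month follow-up come before Table 6-2, and either may include a test. Nor do they support extending the point to patients who finish the Core Phase on drug, whose EOS-CP visit is governed by Table 6-1.

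**Conclusion.** The point holds in a limited form. For females of child-bearing potential who stopped drug for a non-safety reason, follow Table 6-2 and then enter the Extension, the legible protocol shows no required pregnancy test close to the first Extension dose. The first scheduled serum sample comes 12 to 16 days into daily fingolimod, with a result on about days 14 to 18 at the earliest, plus shipping.

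This rests on two assumptions: that no pregnancy row or footnote lies behind the Table 6-2 redactions, and that any test at discontinuation or follow-up is not recent when she re-enters. The second can fail if drug was stopped late in the Core Phase. The interval since the last test cannot be derived without Table 6-1. The documents give no size for the group. It must be small, since safety discontinuations are barred from the Extension.

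Severity is low. The change is still worth making, because it is cheap and does no harm if a hidden EOS-CP test exists.

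**What to change.** Add a footnote to the Table 6-3 pregnancy row, limited to females of child-bearing potential entering from Table 6-2: a negative pregnancy test is required before the Visit 15 dose. Either of these would satisfy it:

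- an on-site urine test at Visit 15; or
- a serum test on the "Hematology/Blood chemistry" draw already marked at Table 6-2 EOS-CP, with the result in hand before dosing and within the 14-day window. Any EOS-CP test already in the plan would count.

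In Extension exclusion 2, in both Section 4.2 and the synopsis, exempt this test from the statement that additional tests are not needed. Do not add a serum test at Visit 15 for everyone.

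The cost is one footnote and one clause in two places. In practice it is one urine test or one extra assay per patient in a small subgroup. The serum option means a wait of at least 2 days plus shipping. These patients are already off study drug, so waiting interrupts no dosing.
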